**Statistical Analysis:**

Assuming dehiscence rates of 3.05% for MAR-CUTIS and 0.85% for Dermabond Advanced, 189 subjects (2:1, 126 MAR-CUTIS versus 63 Dermabond Advanced) ensure a power of 85% to show noninferiority of MAR-CUTIS compared with Dermabond Advanced using a one-sided significance level of  $\alpha = 0.05$  and a Farrington-Manning test given a noninferiority margin of 8%.

The assumed dehiscence rates of 3.05% and 0.85% were derived based on the assumption to have 15% of subjects in the trial with lacerations that have a dehiscence rate of 0.5% for MAR-CUTIS and 0% for Dermabond Advanced and 85% of subjects in the trial with incisions, with dehiscence rates of 3.5% for MAR-CUTIS and 1% for Dermabond Advanced.

The assumed noninferiority margin of 8% is based on an average of dehiscence rates observed in previous studies eg, Siddiqui et al 2013 (dehiscence between 2%-13%), Muncie et al 2018 (dehiscence rates between 0.8-7.5%), and Eymann et al 2010 (dehiscence rates between 2%-24%). Noninferiority versus a placebo would not be ethical in the context of this trial, and thus has been set conservatively versus an approved IMD (Dermabond).

Descriptive statistics for the efficacy parameters will be based on the Full Analysis Set and for the safety and tolerability parameters based on the Safety Analysis Set. Summaries will be provided by treatment and time point (if applicable).

For the primary efficacy endpoint, Maximum-Likelihood estimates will be obtained fitting a logistic regression model to the dehiscence rates using the skin type (types I to III/types IV to VI), age group (2 to 21 years and  $\geq 22$  years), type of wound (incision/laceration) and treatment as explanatory variables. The method of Farrington-Manning (FM) will be applied to determine the variance estimator. Based on the derived Maximum-Likelihood estimates for the dehiscence rates and the FM estimate for the variance, the p-value of the FM test regarding noninferiority and the 90% confidence interval for the difference in dehiscence rates will be determined. The noninferiority of MAR-CUTIS compared with Dermabond Advanced will be established if the upper limit of this confidence interval is below the noninferiority margin of 8%.

A sensitivity analysis will be performed considering the length of incision/laceration in the logistic regression model instead of the wound type. Other sensitivity analyses will be performed as well.

All endpoints other than the primary efficacy endpoint will only be investigated descriptively in an exploratory manner.

---

## 4 LIST OF ABBREVIATIONS

### LIST OF ABBREVIATIONS

ADE	Adverse device effect
AE	Adverse event
CDC	Center for Disease Control and Prevention
CMH	Cochran-Mantel-Haenszel
DD	Device deficiency
eCRF	Electronic case report form
FAS	Full Analysis Set
FM	Farrington-Manning
GCP	Good Clinical Practice
ICF	Informed consent form
ICH	International Council for Harmonisation
ID	Identifier
IEC	Independent Ethics Committee
IMD	Investigational medicinal device
IRB	Institutional Review Board
ISO	International Organization for Standardization
mHCS	Modified Hollander Cosmesis Scale
POSAS	Patient and observer scar assessment scale
PPS	Per Protocol Set
SAE	Serious adverse effect
SAP	Statistical analysis plan

---

## 5 INTRODUCTION

The goal of wound closure is to achieve hemostasis, avoid infection, and restore function to the affected skin area with minimal scarring. The most commonly used methods for wound closure after surgical procedures or traumatic injuries employ staples or sutures. Alternative methods for wound closure include the use of skin adhesives. The application of skin adhesives offers potential advantages over standard staple/suture methods (Smith et al. 2010, Sajid et al. 2009, Dumville et al. 2014):

- Simpler and shorter application procedure.
- Reduced pain intensity.
- Less trauma and disruption of wound's microcirculation.
- No painful injection of local anesthetic.
- Barrier function against microbial penetration into the wound bed.
- No risk of accidental needle stick injury.
- No need for follow-up for removal of sutures.
- Good cosmetic results.

Adhesives have been used in various forms for many years since the first cyanoacrylate adhesives were synthesized (Coover 1959). These early adhesives were appropriate for small superficial lacerations and incisions, but their limited physical properties prevented use in the management of other wounds. In addition, acute and chronic inflammatory reactions were reported to occur (Houston 1969). Further development led to the introduction of the n-2-butylcyanoacrylates that were purer and stronger, but those did not receive widespread acceptance, because their clinical performance was limited by their low tensile strength and brittleness (Bruns 1996; Quinn 1993). More recently, stronger skin adhesives have been developed to increase flexibility and reduce toxicity by combining plasticizers and stabilizers (Quinn 1997). Skin adhesives have been used primarily in emergency rooms and there is increasing support in the literature for their effectiveness in the closure of various traumatic lacerations (Dumville et al. 2014, Farion 2002). Surgeons now also use skin adhesives in the operating room for the closure of surgical skin incisions.

Although skin adhesives may offer some of the advantages listed above, a Cochrane Systematic Review concluded that there is insufficient evidence as to whether covering surgical wounds healing by primary intention with cyanoacrylates adhesives reduces the risk of infections, improves scarring, pain control, subject acceptability or ease of dressing removal. Apart from that, the review showed that sutures are significantly better than cyanoacrylate adhesives for minimizing dehiscence (Dumville et al. 2014). As such, the development of a skin adhesive that affords dehiscence comparable with sutures would offer subjects an alternative method of wound closure which is less burdensome than the use of sutures or staples.

Wound dehiscence is one of the most common complications of surgical wounds and it involves the breaking open of the surgical incision along the suture. Typically, the sutures or closures around wound edges stay intact while new tissue, known as "granulation tissue," starts forming to help heal the wound. However, when wound dehiscence occurs, the edges start to separate and the wound reopens instead of healing.

---

Wound dehiscence can be caused by poor surgical techniques such as improper suturing, overtightened sutures, or inappropriate type of sutures. Wound dehiscence can also be caused by increased stress to the wound area as a result of strenuous exercise, heavy lifting, coughing, laughing, sneezing, vomiting, or bearing down too hard with a bowel movement. In some cases, wound dehiscence could be secondary to wound infection or poor healing as seen in patients with chronic diseases, malnutrition, or weak immune systems. Secondary wound dehiscence can also occur in patients with AIDS, renal disease, diabetes mellitus, and those undergoing chemotherapy or radiotherapy.

Every person who has a surgical wound has a risk of dehiscence, especially in the first 2 weeks after surgery when the tissue is still weak and not completely healed. The 2 most important factors controlling the risk of wound dehiscence are:

- The patient's health status – the risk is higher in patients with a weak immune system, malnutrition, or chronic medical illness.
- The surgical procedure – the risk of dehiscence increases with overtightening of sutures, poor suturing technique, inappropriate surgery site, or suturing material.

The risk is also greater with smoking, obesity, premature postsurgery exercise, heavy lifting, recurrent vomiting, coughing, or an improper diet that leads to constipation.

Any wound dehiscence needs to be treated as a new wound and is a surgical emergency that requires immediate attention. Surgical debridements, antibiotic therapy, reclosure with the appropriate surgical technique, and sutures represent the most appropriate treatments. Finally, the patient's wound should be closely monitored to prevent dehiscence from recurring.

For all the above mentioned reasons, wound dehiscence always needs to be prevented as much as possible.

Therefore, a new, polyurethane-based topical skin adhesive has been developed: MAR-CUTIS. MAR-CUTIS is intended for topical application to close wounds of the skin, such as cuts and wounds from surgical incisions. It consists of a polyurethane-based prepolymer and an amino acid-based hardening agent which are provided in prefilled, double syringes with a mixing cannula and spreader tip.

Information about the preclinical testing as well as known and expected benefits, risks, serious adverse events (SAEs) and reasonably anticipated adverse events (AEs) of MAR-CUTIS are to be found in the Investigator's Brochure.

In particular, there are some predictable AEs (rates) that have been observed with other skin adhesives and can be possibly associated with the use of MAR-CUTIS:

- Infection (3.6%) after wound closure; this also applies to sutures and is not limited to adhesives.
- Dehiscence (2.5%) which is greater in wounds closed with skin adhesive as compared to other methods of wound closure (namely sutures, staples and strips).
- Improper application of the skin adhesive (unknown).

- Allergic reactions (11.5%).
- Other additional risks mentioned in risk management file, eg, pain (6.1%), edema (9.7%), and warmth (1.3%).

Such novel polyurethane-based medical adhesive differs from existing technologies due to its unique composition. The adhesive technology is:

- Fully Synthetic
- Easy to use
- Flexible

Based on polyurethane, it is completely different from existing skin adhesives based on cyanoacrylate. This new component is adhering to the tissue via mechanical and physical adhesion, forming a strong, yet flexible film. There is no reaction with the tissue itself; a strong polymer network is quickly formed and full polymerization is completed after a few minutes.

## 6 STUDY OBJECTIVES

Objectives	Endpoints

Primary Efficacy Objective:
 
 
To compare the dehiscence rate between MAR-CUTIS and Dermabond Advanced between Day 1 and Day 10.
 
	
Primary Efficacy Endpoint:
 
 
Total dehiscence rate of target incision/laceration assessed at the Day 10 visit.
 

Main safety objective:
 
 
To compare the incidence of AEs between MAR-CUTIS and Dermabond Advanced.
 
	
Main safety endpoint:
 
 
Adverse events within 1 month after treatment classified by severity and relatedness to the treatment.
 

Secondary
	

 
To compare the dehiscence rate between MAR-CUTIS and Dermabond Advanced at the Month 1 visit.
 
	
 
Total dehiscence rate of target incision/laceration assessed at the Month 1 or Early Discontinuation visit (if Early Discontinuation occurs before Month 1).
 

 
To compare the incidence of AEs between MAR-CUTIS and Dermabond Advanced at additional study time points.
 
	
 
Adverse events classified by severity and relatedness to the treatment.
 

 
To evaluate the subject satisfaction with the cosmetic outcome after treatment of the surgical incision/laceration with MAR-CUTIS versus Dermabond Advanced.
 
	
 
Subject-completed Patient and Observer Scar Assessment Scale (POSAS) done at the Month 1 and Month 3 visits or at the Early Discontinuation visit (if Early Discontinuation occurs before Month 1).
 


 
To compare the wound infection incidence between both treatment groups.
 
	
 
Wound infection incidence assessed at the Day 10, Month 1, and Month 3 visits or at the Early Discontinuation visit (diagnosed according to the Centers for Disease Control and Prevention [CDC] criteria for surgical site infection [Section 15.1]).
 
Wound infection assessed on a binary scale (“1 - yes” or “0 - no”) for the following criteria: 
 
Presence of erythema
 
Presence of edema
 
Presence of pain at rest
 
Presence of elevated temperature
 
 A total score will be calculated for each subject.
 

 
To evaluate the investigator satisfaction with the cosmetic outcome after the closure of the target surgical incision/laceration with MAR-CUTIS versus Dermabond Advanced.
 
	
 
Investigator-completed POSAS done at the Month 1 and Month 3 visits or at the Early Discontinuation visit (if Early Discontinuation occurs before Month 1).
 

	

Investigator-completed Modified Hollander Cosmesis Scale (mHCS) done at the Day 10 and Month 1 visits or at the Early Discontinuation visit (if Early Discontinuation occurs before Month 1).

To evaluate the subject comfort with the device during and after treatment with MAR-CUTIS versus Dermabond Advanced.

	

A questionnaire related to subject experience and satisfaction with the device completed by the subject at the Day 10 and Month 1 visits or at the Early Discontinuation visit (if Early Discontinuation occurs before Month 1).

A subject-related questionnaire completed by the investigator at the Day 0 and Month 1 visits or at the Early Discontinuation visit (if Early Discontinuation occurs before Month 1).



To evaluate the investigator overall satisfaction and ease of use with the device during and after the closure of the target surgical incision/laceration with MAR-CUTIS or Dermabond Advanced.

	

A product-related questionnaire completed by investigators at the Month 1 or Early Discontinuation visit (if Early Discontinuation occurs before Month 1).

---

[figure not shown]
## 7 INVESTIGATIONAL PLAN

### 7.1 Overall Study Design and Plan: Description

This is a randomized, open-label, multi-center, comparator-controlled clinical study to compare MAR-CUTIS with Dermabond Advanced in closure of surgical incisions  $\geq 6$  to  $\leq 15$  cm and lacerations  $\leq 15$  cm. A total of 189 subjects will be treated (defined as study product applied to the wound). Only subjects that are withdrawn from the study due to product failure at the time of application (see Section 7.3.4) will be replaced. Subjects will be randomized 2:1 to MAR-CUTIS or Dermabond Advanced. Screening and baseline (randomization) can occur on the same day. Application of the investigational medical device (IMD) occurs on Day 0 with wound evaluation occurring on Day 1, Day 10, Month 1, and Month 3/Early Discontinuation. Training on the application of both devices will be provided.

#### 7.1.1 Study Design

Figure 8.1 Study Design

### 7.1.2 Schedule of Assessments

	D -21 to 0	D0	D1	D10	Month 1	Month 3	ED
Visit Window			12 hours up to 36 hours after application	±2 days	±7 days	±14 days	
Obtain written informed consent/assent	X						
Check inclusion/exclusion criteria	X	X					
Record demographic data and medical/surgical history a	X						
Perform a urine $\beta$ -hCG pregnancy test (if applicable)		X					
Allocate subject to treatment and issue a diary		X					
Application of device		X					
Document prior (within the last 2 weeks) and concomitant medication intake (including steroids, immunosuppressants, chemotherapy, anticoagulants, antibiotics. Excluding related to intraoperative anesthesia)	X	X	X	X	X	X	X
Record of adverse events	X	X	X	X	X	X	X
Record of incidents and device performance, device-related complaints		X	X	X	X	X	X
Evaluation of incision/laceration (incidence and grading)		X					
Evaluation of dehiscence			X	X	X		X d
Evaluation of wound infection				X	X	X	X
mHCS completed by investigator				X	X		X d
POSAS completed by subject and investigator					X	X	X d
Subject-completed satisfaction questionnaire				X	X		X d
Subject-related questionnaire completed by investigator c		X			X		X d
Product-related questionnaire completed by investigator					X b		X d
Subject diary collection					X		X d

Abbreviations:  $\beta$ -hCG=beta human chorionic gonadotropin; D=Day; ED=early discontinuation; mHCS= Modified Hollander Cosmesis Scale; POSAS= Patient and Observer Scar Assessment Scale.

---

a In particular, the following information will be collected: body mass index, medical history (including diabetes mellitus, chronic obstructive pulmonary disorder, hematological and vascular disorders, disorders of immune system, congestive heart failure, cardiovascular disease), concomitant medications (excluding related to intraoperative anesthesia), smoking, alcohol abuse.

b The product-related questionnaire is completed by the investigator only once per site when the last subject randomized at the site completes the Month 1 visit.

c Also completed if there is premature removal of the adhesive.

d Only to be performed if Early Discontinuation is before the Month 1 Visit or if the questionnaire has not previously been completed/if the diary has not previously been collected.

---

## 7.2 Discussion of Study Design

### 7.2.1 Study Design

The study will include 3 levels of stratification:

- By wound type (lacerations and incisions): approximately 40 subjects with lacerations will be randomized.
- By skin type according to the Fitzpatrick classification (types I to III versus types IV to VI): approximately 40 subjects with skin types IV to VI will be randomized; approximately 20 subjects from this cohort will have skin types V to VI.
- By age group (2 to 21 years of age and  $\geq 22$  years of age): approximately 30 subjects in the 2 to 21 age group will be randomized. To ensure that the pediatric population is not dominated by an adolescent sub-group, approximately 5 subjects aged 15 to  $< 22$  years will be included.

### Screening and Randomization

Only one incision/laceration will be treated with the IMD. If a subject has more than one incision/laceration, the target wound will be the one with the greatest length (ie, the longest) that meets the study entry criteria. If the length of 2 or more wounds is equal, the investigator can choose either of them to be the target wound.

The incision/laceration will be prepared for closure as per the standard of care at a treating hospital. The investigator will assess the need and perform closure of deep tissue layers as necessary before proceeding with the closure of the last (dermal) layer with the IMD.

All lacerations will first be assessed for the need of deep suturing and/or debridement; this information will be recorded in the electronic case report form (eCRF). Wounds that require debridement and/or deep suturing will be treated according to the local practice of the investigator and only at the time of skin closure will the lacerations be randomized into 1 of the 2 study treatment arms. Wounds that do not require deep suturing and/or debridement will be randomized immediately.

Re-screening is not allowed in the study.

### Treatment Phase

Use of Dermabond Advance will be according to Instructions for Use (Section 15.2). Wounds closed with Dermabond Advanced will be prepared in a standard manner. They will be cleaned with an antiseptic solution (which will be recorded in the eCRF), patted dry with dry, sterile gauze, and hemostasis will need to be achieved prior to wound closure (eg, by pressure application or use of local vasoconstrictors). Wound edges will be approximated by fingers of forceps and Dermabond Advanced will be applied in one continuous layer onto a dry wound through painting motions, taking care not to apply adhesive between the wound edges. Applying a second layer is not required or recommended. If a second layer of Dermabond Advanced is applied, or if large droplets of liquid are not spread thinly, the subject may experience an increased sensation of heat or discomfort. The wound will be held for 60 seconds to allow for complete polymerization. The wound may or may not be covered with a protective dressing thereafter.

Wounds closed with MAR-CUTIS will be prepared in a standard manner. They will be cleansed with an antiseptic solution (which will be recorded in the eCRF), patted dry with dry, sterile gauze, and hemostasis will need to be achieved prior to wound closure (eg, by pressure application or use of local vasoconstrictors). The use of peroxide-containing antiseptics is not recommended to be applied directly on the MAR-CUTIS strip as they may provoke cracking of the strip. These products however may be used for preparing the wound for closure. In addition, iodine-containing products may be used as necessary but they may stain the glue strip making it non-transparent. Wound edges will be approximated by fingers of forceps and MAR-CUTIS will be applied in one 1 to 2 mm thick layer ensuring that at least 1 cm of the glue is applied over the length of the wound on each side. The amount of the glue applied will be calculated such that one 5-mL syringe covers up to 8 cm of wound length (giving a total of 10 cm per syringe). For wounds >8 cm, 2 syringes will be needed. The wound will be held for approximately 30 seconds to allow for initial polymerization. Only for the pediatric population, the maximum number of syringes per day is limited based on the body weight as shown in the table below:

Body Weight	Number of MAR-CUTIS Syringes
10 to <15 kg	Maximum of 1 syringe
15 kg and above	Maximum of 2 syringes

A protective dressing may be applied after 3 minutes and instructions will be given to the subject on wound protection and showering as MAR-CUTIS requires moisture protection during showering.

If necessary, further dressing and wound management will be performed in accordance with the local practice.

Evaluation of all wounds will occur on Day 1, Day 10, Month 1, and Month 3/Early Discontinuation.

All subjects (or subject legal guardians in case of a pediatric subject) will be issued a subject's diary to record any wound exposure to water and any complaints. The diaries will be collected at the Month 1 study visit and analyzed descriptively.

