### **7.4 Investigational Medical Device**

#### **7.4.1 Investigational Medical Device Applied**

MAR-CUTIS is a polyurethane-based skin adhesive. At the time of use, the 2 components in the syringe are mixed in the mixing cannula. Complete hardening occurs about 5 minutes after application to the skin. The adhesive result can be corrected in the first 30 seconds. MAR-CUTIS is distributed sterile and is intended for single use. The product is used for topical closure of incisions and surgical wounds, replacing the last dermal suture line. It is not intended for intra-abdominal use and/or as a substitute for subcutaneous sutures. It should not be used after the expiration date and/or if the sterile packaging has been opened or damaged.

Dermabond Advanced is a topical skin adhesive used to hold closed easily approximated skin edges of wounds from surgical incisions, including incisions from minimally invasive surgery, and simple, thoroughly cleansed, trauma-induced lacerations.

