### 7.4.5 Application in the Study

Detailed instruction and a training video on the application of MAR-CUTIS will be provided to each investigational site. MAR-CUTIS will be applied in one 1 to 2 mm thick layer, ensuring that at least 1 cm of the glue is applied over the length of the wound on each side.

---

The amount of the glue applied will be calculated such that one 5-mL syringe covers approximately 8 cm of wound length (giving a total of 10 cm per syringe). For wounds >8 cm, 2 syringes will be required. The wound will be held for approximately 30 seconds to allow for initial polymerization. Only for the pediatric population, the maximum number of syringes per day is limited based on the body weight as shown in the table below:

Body Weight	Number of MAR-CUTIS Syringes
10 to <15 kg	Maximum of 1 syringe
15 kg and above	Maximum of 2 syringes

Detailed instruction and a training video on Dermabond Advanced application will also be provided to each investigational site. Use of Dermabond Advanced will be according to Instructions for Use (Section 15.2). Dermabond Advanced will be applied in one continuous layer onto a dry wound through painting motions, taking care not to apply adhesive between the wound edges. Applying a second layer is not required or recommended. If a second layer of Dermabond Advanced is applied or if large droplets of liquid are not spread thinly, the subject may experience an increased sensation of heat or discomfort. The wound will be held for 60 seconds to allow for complete polymerization.

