### DIRECTIONS FOR USE

1. The application of DERMABOND ADVANCED™ Adhesive requires thorough wound cleansing. Follow standard surgical practice for wound preparation before application of DERMABOND ADVANCED™ Adhesive (i.e., anesthetize, irrigate, debride, assure hemostasis, and close deep layers making sure that the wound edges can be easily approximated).
2. Pat the wound dry with dry, sterile gauze to assure direct contact of the DERMABOND ADVANCED™ Adhesive to the skin. Moisture accelerates DERMABOND ADVANCED™ Adhesive's polymerization and may affect wound closure results.
3. To prevent inadvertent flow of liquid DERMABOND ADVANCED™ Adhesive to unintended areas of the body, the wound should be maintained in a horizontal position and the DERMABOND ADVANCED™ Adhesive should be applied from above the wound.
4. DERMABOND ADVANCED™ Adhesive should be used immediately after crushing the ampoule, since the liquid DERMABOND ADVANCED™ Adhesive will flow freely from the tip for only a few minutes.
5. Refer to the instructions on the package for crushing the ampoule and expressing the liquid adhesive. Remove the applicator from the blister package. Hold the applicator with the thumb and a finger, away from the patient to prevent any unintentional placement of the liquid DERMABOND ADVANCED™ Adhesive into the wound or on the patient. With the applicator tip pointing downward, apply pressure at the midpoint of the bulb to crush the ampoule. Gently squeeze the applicator sufficiently to moisten the internal filter with the liquid adhesive. Stop squeezing and allow the liquid DERMABOND ADVANCED™ Adhesive to draw back into the applicator.
6. Approximate the wound edges with gloved fingers or sterile forceps. Slowly apply the liquid DERMABOND ADVANCED™ Adhesive in one continuous layer to the surface of the approximated wound edges using a gentle brushing motion. Maintain manual approximation of the wound edges for approximately 60 seconds after the application. The width of the layer can be increased or decreased by adjusting the amount of pressure applied to the bulb during application. Full apposition strength is expected to be achieved within minutes after the adhesive is applied. Full polymerization is expected when the DERMABOND ADVANCED™ Adhesive layer is no longer sticky.
7. Do not apply liquid or ointment medications onto wounds closed with DERMABOND ADVANCED™ Adhesive because these substances can weaken the polymerized film, leading to skin edge separation.

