8. Protective dry dressings such as gauze may be applied only after DERMABOND ADVANCED™ Adhesive film is completely polymerized: not tacky to the touch after a few minutes. Allow the DERMABOND ADVANCED™ Adhesive to fully polymerize before applying a bandage.

9. Patients should be instructed to not pick at the polymerized film of DERMABOND ADVANCED™ Adhesive. Picking at the film can disrupt its adhesion to the skin and cause skin edge separation.
10. Patients should be instructed that until the polymerized film of DERMABOND ADVANCED™ Adhesive has sloughed naturally (usually in 5–10 days), there should be only transient wetting of the treatment site. Patients may immediately shower or bathe the site gently as directed by their physician. The site should not be scrubbed, soaked, or exposed to prolonged wetness until after the film has sloughed naturally and the physician has determined that the wound is adequately healed. Patients should be instructed not to swim during this period.
11. If removal of DERMABOND ADVANCED™ Adhesive is necessary for any reason, carefully apply petroleum jelly or acetone to the DERMABOND ADVANCED™ Adhesive film to help loosen the bond. Peel off the film; do not pull the skin edges apart.

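### The protocol body equates Dermabond's 60-second hold with complete polymerization and then permits a dressing, contradicting the appended instructions it makes binding

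*Protocol*

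**What the plan says.** The Dermabond paragraph under Treatment Phase (protocol Section 7.2.1) begins by pointing to the manufacturer's instructions: "Use of Dermabond Advance will be according to Instructions for Use (Section 15.2"). It then describes how the product is applied and continues: "wound will be held for 60 seconds to allow for complete polymerization. The wound may or may not be covered with a protective dressing thereafter". It gives no waiting time and no check of the film between the hold and the dressing.

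Section 7.4.5 also refers to Section 15.2 and repeats the first half of that statement: "The wound will be held for 60 seconds to allow for complete polymerization". It says nothing about dressings. It adds that each site will receive detailed instruction and a training video on applying the product.

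The Instructions for Use are reproduced in Section 15.2. Under Directions for Use, item 6 asks for the wound edges to be kept together manually for about 60 seconds. It then says "Full apposition strength is expected to be achieved within minutes after the adhesive is applied" and ties full polymerization to the layer having stopped being sticky. Item 8 permits a dry protective dressing only after the "film is completely polymerized: not tacky to the touch after a few minutes".

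The SAP does not settle the matter. Its Section 12.3 mentions instructions and training on both products but gives no setting or dressing times.

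**The concern.** The 60-second hold carries two meanings. In the body of the protocol it is the time to complete polymerization. In the appendix it is the time for which the edges are held, and complete polymerization is a later state judged by touch.

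This matters because complete polymerization is the exact condition that Section 15.2 sets for a dressing. A reader of Section 7.2.1 is told that the condition is met at 60 seconds, and the next sentence allows the dressing. On that reading the tack check looks unnecessary. A control wound dressed just after the hold would then comply with Section 7.2.1 and depart from Section 15.2, and the text alone does not say whether that is a deviation.

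The instruction governs how the comparator is applied in an open-label trial whose primary endpoint is dehiscence of the target wound up to Day 10. The protocol relies on training of device users to limit bias in that endpoint (Sections 7.4.7 and 10.1.3.1.2), so the text on which training rests should not contradict itself.

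**Working it through.** No formula applies. The plan states no figure that depends on this point, and its sample size, margin and power do not use it. The check is a comparison of texts.

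| Question | Protocol body (7.2.1, 7.4.5) | Instructions for Use (15.2) |
|---|---|---|
| How long is the wound held? | 60 seconds | About 60 seconds (item 6) |
| What is the hold for? | Complete polymerization | Manual approximation of the edges (item 6) |
| When is polymerization complete? | At the end of the hold | When the layer has stopped being sticky (item 6); a few minutes expected (item 8) |
| When may a dressing go on? | After the hold; no wait or check given (7.2.1 only) | Only when completely polymerized and not tacky (item 8) |

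1. **Length of the hold.** The two texts agree, so there is no conflict here.
2. **Meaning of the hold.** They disagree. The body could be excused as loose wording if it used the term casually, but Section 7.2.1 separates two stages. It speaks of initial polymerization for MAR-CUTIS after about 30 seconds and of complete polymerization for Dermabond after 60 seconds. The word complete therefore carries weight.
3. **Time to complete polymerization.** The body says 60 seconds. The instructions say minutes, with a test by touch. That test describes a state; the few minutes are the expected time to reach it, not a fixed wait.
4. **Permission to dress.** Both texts follow the same order: polymerize first, then dress if wanted. Because they disagree on when the first step ends, they disagree on when the second may begin.
5. **Effect of the cross-reference.** Both sections make Section 15.2 binding and do not say which text prevails. Two incompatible statements therefore apply together.

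The documents do not give the share of control wounds that would be dressed, the share dressed before the film has set, or the effect of doing so on dehiscence. No consequence for the primary endpoint can be calculated from them.

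**The case against.** The strongest reply is that the correct condition is already in the protocol. The Dermabond paragraph opens by sending the site to Section 15.2, and item 8 there states when a dressing may be applied. The sentence "The wound may or may not be covered with a protective dressing thereafter" sets no time and does not cancel that condition. Sites are also trained on application. On this view, a dressing reaches a tacky film only if a site overlooks the opening sentence.

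Part of this stands. A site that follows both texts would check for tack, so early dressing is a possibility and not a planned practice. But the reply does not remove the contradiction. The body tells the reader that the condition in item 8 is satisfied at 60 seconds, which gives a careful reader a reason to think both texts have been followed.

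Three stronger readings are tempting, and the documents do not support them.

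- **That MAR-CUTIS has the same fault.** Section 7.2.1 says "A protective dressing may be applied after 3 minutes", while Section 7.4.1 says "Complete hardening occurs about 5 minutes after application to the skin". One is a dressing time and the other a product property. Nothing in the protocol requires MAR-CUTIS to be fully hardened before it is dressed, so the two can both be true. Item 8 belongs to a different product and cannot be carried over.
- **That only the test arm has an explicit wait before dressing.** This is true only if Section 15.2 is ignored. Through Section 15.2 the control arm has an explicit condition too.
- **That the conflict pushes the result toward noninferiority by a known amount.** With 63 planned control subjects, one extra control dehiscence shifts the difference by 1/63 = 1.6 percentage points, against a margin of 8. That is the weight of any single control event, whatever its cause, and does not measure this issue. Section 15.2 links separation of the skin edges to picking at the film and to liquids or ointments, not to early dressing.

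**Conclusion.** The point holds for the Dermabond text. Sections 7.2.1 and 7.4.5 contradict Section 15.2 on what the 60-second hold achieves, and Section 7.2.1 builds a dressing permission on that statement. The operating instruction for the comparator is therefore wrong as written, in the sense that a site cannot rely on every part of it at once.

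The size is a gap in wording: 60 seconds in the body against a few minutes and a tack check in the appendix. No bias, in size or direction, can be stated for the primary comparison, and the sample size and margin are unaffected.

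The conclusion assumes that Section 15.2 is meant to bind sites, as both sections say. It also assumes that the training material, which is not among the documents, does not already resolve the conflict. If it does, the practical risk is smaller, but the protocol text still needs correcting. This review takes no view on which timing is right.

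**What to change.** Reconcile the Treatment Phase text of Section 7.2.1 and the application text of Section 7.4.5 with items 6 and 8 of the Directions for Use in Section 15.2. After the change:

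- the 60-second hold should have one stated meaning wherever it appears;
- the condition for placing a dressing on a Dermabond wound should be stated once, with other places referring to it;
- the instruction and training video for sites should use the same text.

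The sponsor decides which timing and condition apply.

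The cost is a wording change in two protocol sections and a check of the training material. It needs no extra visits, subjects or analyses. Recording Day 0 dressing and its timing may be useful, but it is not part of this correction: the case report form is not among the documents, so it may already be captured.
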